#### 9.4.2 Time to Death, Reoperation, and Explant

Time to death from the date of operation will be analyzed by the method of Kaplan and Meier. Time to reoperation from the date of operation as well as time to explant from the date of reoperation will be similarly analyzed. For time to explant and time to reoperation, the time to *first* explant or reoperation will be calculated for those subjects requiring explant or reoperation. These analyses will also be reported for the entire study cohort and also stratified by valve size and valve model. Analyses for time to explant and time to reoperation will also be stratified by fatal versus non-fatal events.

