#### 3.3.2 Secondary Safety Endpoints

Secondary safety endpoints will include early and late linearized and actuarial analysis of the following:

- Thromboembolism
- Valve thrombosis
- All hemorrhage
- Major hemorrhage

This document and the information contained herein is considered Proprietary and Confidential and may not be reproduced, used or disclosed without written permission from Edwards Lifesciences LLC.

- All perivalvular leak
- Major perivalvular leak
- Endocarditis
- Hemolysis
- Structural valve deterioration
- Non-structural valve dysfunction
- Reoperation
- Explant
- Death
- Valve-related death

Blood studies including white blood count, red blood count, hematocrit, plasma free hemoglobin (or haptoglobin and SLDH), platelet and reticulocyte counts will be used to evaluate the rate of hemolysis and adverse events at the 6 month, 1 year and annual follow-up visits.

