## 8.1 Potential Risks

Risks known to be associated with the use of bioprothestic heart valves and valve replacement procedures may include, but are not limited to the following: angina, cardiac arrhythmia, endocarditis, heart failure, hemolysis, hemolytic anemia, hemorrhage (bleeding), local and/or systemic infection, myocardial infarction, prothetic leaflet entrapment, prosthetic nonstructural dysfunction, prosthetic pannus, prosthesis perivalvular leak, prosthetic regurgitation, prosthetic structural deterioration, prosthesis thrombosis, thromboembolism, multi-system organ failure, non-cerebral blood clot, pericardial effusion or cardiac tamponade, respiratory failure, stroke or transient ischemic attack

Additional risks associated with the use of Carpentier-Edwards PERIMOUNT mitral valve models have been compiled from critical literature reviews and from reports received through the Edwards Lifesciences complaint handling system. These risks may include but are not limited to the following: stenosis, regurgitation through an incompetent valve, ventricular perforation by stent posts, malfunctions of the valve due to distortion at implant, and fracture of the wireform frame.

As a result of these complications, a study subject may require:

- reoperation or
- explant and replacement of the Edwards Magna Mitral valve,

OR may experience:

- permanent disability
- death

This document and the information contained herein is considered Proprietary and Confidential and may not be reproduced, used or disclosed without written permission from Edwards Lifesciences LLC.

Although the Magna Mitral valve models have undergone extensive bench top and animal testing in accordance with the FDA guidance document, not all models required clinical trial data due to minor modifications.

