#### Reintervention

*Reintervention* is any surgical or percutaneous interventional catheter procedure that repairs, otherwise alters or adjusts, or replaces a previously implanted prosthesis or repaired valve. In addition to surgical reoperations, enzymatic, balloon dilatation, interventional manipulation, repositioning, or retrieval, and other catheter-based interventions for valve-related complications are also considered *reinterventions*. Indications for *reintervention* must be reported. Open surgical and percutaneous catheter *reinterventions* should be listed separately.

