#### Table 2: Observed Adverse Event Rates (Model 6900P) All patients analyzed: N = 209 Cumulative follow-up: 873.18 total pt-vrs.

	Early	Events	Late	Events 	Freedom from Event (%) [95% CI] 	
Complication	n 	%	n	%/pt-yr	1 year	5 years
Mortality (all)	3	1.4	45	5.3	93.2 [88.8, 95.9]	74.4 [66.9, 80.5]
Valve-related events						
Mortality (valve-related)	1	0.5	12	1.4	98.5 [95.5, 99.5]	92.0 [86.2, 95.5]
Explants	1	0.5	8	0.9	97.5 [94.0, 98.9]	96.5 [92.2, 98.5]
Reoperations	0	0.0	0	0.0	100.0 [100, 100]	100.0 [100, 100]
Bleeding Events	5	2.4	13	1.5	96.1 [92.3, 98.0]	91.9 [86.5, 95.2]
Endocarditis	1	0.5	3	0.4	99.5 [96.6, 99.9]	97.1 [92.1, 98.9]
Nonstructural dysfunction	0	0.0	1	0.1	99.5 [96.4, 99.9]	99.5 [96.4, 99.9]
Perivalvular leak (all)	1	0.5	2	0.2	99.5 [96.7, 99.9]	98.4 [95.2, 99.5]
Structural valve deterioration	0	0.0	2	0.2	100.0 [100, 100]	99.0 [93.2, 99.9]
Thromboembolism	4	1.9	12	1.4	97.0 [93.5, 98.7]	91.3 [85.8, 94.7]
Thrombosis	0	0.0	0	0.0	100.0 [100, 100]	100.0 [100, 100]

Notes:

1. Late event rates were calculated as linearized rates (%/pt-yr) based on 856.24 late patient-years

(> 30 days postoperatively).

2. Freedom from event rates were calculated using the Kaplan-Meier method. Greenwood's formula was used for calculation of the standard errors of these estimates 3 n = number of events

Table 3: Preoperative Patient Demographics (Model 6900)					
		Study Characteristics (N = 363; 1100 total pt-yrs.)			
Variable	Category	n	% (n/N) 		
Age at implant (N = 363)	$Mean\pmSD$	66.1 ± 10.7			
Gender	Female/Male	212/151	58.4%/41.6%		
Diagnosis/Etiology	None	30	8.3%		
	Stenosis	91	25.1%		

Note

1. n = number of patients in each category: N = total number of study patients.

Regurgitation

Mixed Disease

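### Sections 3.3.2 and 9.4.2 do not say whether an explant counts as a reoperation, so the reoperation curve could leave out valve replacements

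*Combined protocol and SAP*

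**What the plan says.** Among the secondary safety endpoints in Section 3.3.2, the list runs "Reoperation - Explant - Death". Each is to have early and late linearized rates and an actuarial analysis.

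Section 9.4.2 sets the time-to-event rule: "Time to reoperation from the date of operation as well as time to explant from the date of reoperation will be similarly analyzed". Only the first event of each kind is used, and its time "will be calculated for those subjects requiring explant or reoperation". Results are also split by valve size, by valve model, and by fatal versus non-fatal events.

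Two other places bear on the meaning of the terms:

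- Section 8.1 names two consequences of complications, joined by an or: reoperation, and "explant and replacement of the Edwards Magna Mitral valve".
- Appendix 1, the reporting guideline that Section 6.1.2 adopts for assessing adverse events, defines Reintervention as "any surgical or percutaneous interventional catheter procedure that repairs, otherwise alters or adjusts, or replaces a previously implanted prosthesis or repaired valve". It asks for open and catheter procedures to be listed separately.

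Appendix 8, the protocol's own event definitions, has no entry for reoperation or explant. No section maps the Appendix 1 term onto either endpoint.

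**The concern.** The two hints in the protocol pull in opposite directions. Section 8.1 treats reoperation and explant as alternatives, so an explant would not be a reoperation. Section 9.4.2 starts the explant clock at reoperation, so every explant would need a reoperation at or before it. Taken literally, neither reading gives a usable analysis. If an explant is not a reoperation, a subject with an explant alone has no time origin. If the explant is itself the reoperation, the elapsed time is zero.

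Clinicians will read freedom from reoperation as freedom from another operation on the valve. If explants are left out, that curve omits valve replacements, which are central to the durability question. Under Section 6.8 a subject leaves the study 30 days after explant or once device-related serious events resolve. An explant not counted as a reoperation would therefore probably be censored in the reoperation curve. That is an inference, because no censoring rule is stated.

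**Working it through.** **Inputs.** Model 6900P: Table 2 of the 7300TFX instructions for use (Appendix 4), repeated as Table 4 of Appendix 9; N = 209 and 856.24 late patient-years. Model 6900: Table 1 of the same instructions, repeated as Table 3 of Appendix 9; N = 363 and 1072.5 late patient-years. Stated exposure: 808 subject-years (Section 9.1).

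**Formulas.** Early % = early events / N. Late rate = 100 × late events / late patient-years.

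**Step 1: reproduce the printed figures.**

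| Row | Early | Late, % per patient-year | Total events | 5-year freedom (printed) |
|---|---|---|---|---|
| 6900P explant | 1/209 = 0.48% (printed 0.5) | 8/856.24 = 0.93 (0.9) | 9 | 96.5% |
| 6900P reoperation | 0/209 = 0% (0.0) | 0/856.24 = 0 (0.0) | 0 | 100% |
| 6900 explant | 0/363 = 0% (0) | 8/1072.5 = 0.75 (0.7) | 8 | 96.7% |
| 6900 reoperation | 2/363 = 0.55% (0.6) | 12/1072.5 = 1.12 (1.1) | 14 | 95.1% |

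All agree with the tables to rounding.

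**Step 2: what 6900P shows.** With 9 explants and 0 reoperations, no explant was counted as a reoperation. Had all nine counted, reoperations would be 9: 0.48% early and 0.93% per patient-year late (exact Poisson 95% CI 0.40 to 1.84). Freedom from reoperation would then be at most the explant figures, 97.5% at 1 year and 96.5% at 5 years, against 100% printed at both. The 5-year gap within this table is 100 − 96.5 = 3.5 points.

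**Step 3: what 6900 shows.** If its 8 explants lie within the 14 reoperations, there were 14 events in all and the late rate is 12/1072.5 = 1.12. If the categories are disjoint, there were 14 + 8 = 22 events and the late rate is (12 + 8)/1072.5 = 1.86. The table fits both.

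**Step 4: scale to this study.** Expected late explants = late rate × subject-years.

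- At 808: 0.746% × 808 = 6.0, and 0.934% × 808 = 7.5.
- At about 1,500 (assumption): 0.746% × 1,500 = 11.2, and 0.934% × 1,500 = 14.0.

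The 1,500 is not a protocol figure. It takes 250 subjects with a constant hazard fitted to the 56% eight-year survival in Section 9.1 and ignores loss to follow-up: 250 × 8 × (1 − 0.56)/(−ln 0.56) = 880/0.580 ≈ 1,518. The 808 is a floor, because Section 9.1 adds the life-years of subjects who do not reach 8 years.

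**The case against.** The case for leaving the text alone has several parts.

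- **No removal is lost.** Explant has its own linearized and actuarial results, so a reader sees it beside reoperation. This stands. The problem is what the reoperation figure means, not hidden explants.
- **The documents already lean one way.** Section 9.4.2 ties explant to reoperation, and Section 6.1.2 points to Appendix 1, whose Reintervention covers replacement. The adverse event form puts study-valve reoperation and other study-valve intervention in one box that refers to the explant report. These are fair pointers. None is a rule for the two endpoints, and Section 8.1 points the other way. The form does mean that catheter procedures have a place in data collection, so one cannot say they are bound to fall outside both endpoints.
- **The evidence comes from another valve's study.** True. It shows what can happen, not what this study will report.
- **An explant need not mean a second operation.** The operative form allows an explant at the index procedure, and the 6900P table does not say when or how its nine valves came out. That all nine were surgically replaced later is an inference. Section 6.8 gives it some support by distinguishing explantation from autopsy and describing follow-up after explant.

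A reader might also infer that the sponsor's two tables use incompatible conventions, so that at least 3.5 points of the 5-year difference between models (95.1% against 100%) is definitional. The documents do not support this. The 6900 counts fit disjoint categories as well as nested ones, and if they are disjoint the two tables share one convention.

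**Conclusion.** The concern holds as a gap in endpoint definition that should be closed. The plan analyses two overlapping endpoints without an overlap rule, its own hints conflict, and a predecessor report shows a convention under which freedom from reoperation reads 100% while valves were being explanted.

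The firm size is within 6900P: 100% as printed against at most 96.5% at 5 years if explants count. It would be somewhat higher than 96.5% if any of the nine removals were at the index operation or autopsy and were excluded. For this study, about 6 to 7.5 late explants at 808 subject-years could be in or out of the reoperation curve, rising to about 11 to 14 under the assumed 1,500. Both ranges assume that the predecessor rates carry over to the study valves.

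Neither endpoint carries a hypothesis test or threshold, so the effect is on how durability is described.

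**What to change.** In Section 9.4.2 and Appendix 8:

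1. Define Reoperation using the Appendix 1 Reintervention wording, limited to surgical or catheter procedures after the index operation that repair, alter or replace the study mitral valve.
2. Count every explant after the index operation, other than at autopsy, as a reoperation. Keep Explant as its own reported subset.
3. Report open and catheter procedures separately, as Appendix 1 asks.
4. Time both endpoints from the implant operation, replacing the present origin for explant.
5. Add a data check: among post-index, non-autopsy events, freedom from reoperation should not exceed freedom from explant. Back it with a subject-level check that each such explant has a reoperation dated no later, because estimated curves can cross under heavy late censoring even when the data are right.

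The cost is a few sentences. The events are already collected on the adverse event form, although its single box for study-valve procedures means that the open/catheter split may have to come from the event narrative. The downside is a less favourable reoperation figure that is not directly comparable with the 6900P table. A footnote should say so.

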#### 9.4.3 Nonstructural Valve Dysfunction and Structural Valve Deterioration

The percentage of subjects experiencing nonstructural valve dysfunction and structural valve deterioration within the early post-operative period (within 30 days of implant) will be reported. Linearized rates will be used to summarize nonstructural valve dysfunction and structural valve deterioration for the late (>30 days) post-operative period. The linearized rates will be reported as the number of nonstructural valve dysfunctions and structural valve deteriorations occurring after the early post-operative period per year of subject exposure. The 30-day frequency and linearized rate for nonstructural deterioration and structural dysfunction will be stratified by the nature of the dysfunction. These analyses will be reported for the entire study cohort and also stratified by valve size and valve model.

## 9.5 Effectiveness Analysis

The effectiveness analyses will be reported for the entire study cohort and also stratified by valve size according to the Tissue Annulus Diameter (TAD) and valve model (7000/7000 TFX ,7200 and 7300/7300 TFX).

This document and the information contained herein is considered Proprietary and Confidential and may not be reproduced, used or disclosed without written permission from Edwards Lifesciences LLC.

#### 9.5.1 Subject Functional Classification

Subjects will be stratified according to the NYHA classification preoperatively, at 6 months and annually post implant for 8 years. The distribution (numbers of subjects and percentages) in the various NYHA classes with be tabulated at each follow-up interval. The percentage of the subjects in NYHA Classes I or II at 8 years post implant will be calculated to determine if it is  $\geq$  75% using a one - sided Binomial exact test. This analysis will also be reported stratified by valve size and valve model.

## 9.5.2 Hemodynamic Performance

Echocardiography data will be obtained preoperatively, early postoperatively and/or discharge, at 6-months and at 1, 2, 4, 6 and 8 year follow-ups. Descriptive statistics for the continuous echo variables and change from baseline (e.g. mean, standard deviation, and range) will be categorized by time interval and valve size. Regurgitation data will be summarized using frequency at each severity level by time interval and valve size. Improvement in regurgitation at one year will be analyzed via the Jonckheere-Terpstra test. Change at one year from baseline for all other hemodynamic outcomes will be analyzed using paired *t*-tests. These analyses will also be reported for the entire study cohort and also stratified by valve model.

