#### **Table 2: Revised Study Reporting Time**

#### Justification for Change in the Study Reporting Time

As of November 4, 2013, a total of 249 patients had a study valve in place at discharge. Therefore, only one (1) additional subject must be implanted between now and December 31, 2014, to meet the protocol requirement of 250 subjects implanted. Of the minimum 250 implanted subjects required per revision H of study protocol (2006-05), a minimum of 101 subjects must be followed for eight (8) years. As of November 4, 2013, we have lost the ability to follow 55 patients either due to death, withdrawal or removal of the study valve. This leaves 203 who can potentially make it to the eight (8) year follow up. Currently, the longest recorded follow-up is five (5) years. Therefore, it will be another three (3) years before the first patient reaches the 8-year follow-up visit and up to six (6) years to achieve 101 patients with eight (8)

This document and the information contained herein is considered Proprietary and Confidential and may not be reproduced, used or disclosed without written permission from Edwards Lifesciences LLC.

year follow-up data. As a result, Edwards anticipates the **final study report** will be submitted in December 2020.

Location	Protocol Revision	Revision Date	Valve Model No(s).
United States/Europe (Not implemented)	Revision A	January 23, 2007	7000/7000TFX
Europe	Revision B.	May 23, 2007	7000/7000TFX
United States/Europe (Not implemented)	Revision C	July 17, 2007	7000/7000TFX
United States/Europe	Revision D	September 25, 2008	7000/7000TFX
United States/Europe	Revision E	January 23, 2009	7000/7000TFX
United States (Northwestern University only)	Revision F	November 24, 2009	7200TFX
United States (Not implemented)	Revision G	September 17, 2010	7300/7300TFX
United States/Europe	Revision H	May 24, 2011	7000/7000TFX/ 7300/7300TFX

Table 3. Study Enrollment by Protocol Revision by Valve Model

Edwards continues to actively review study recruitment procedures in an ongoing effort to improve study enrollment rates and complete the study in a timely fashion.

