## 9.0 STATISTICAL ANALYSIS

Please refer to Sections 11.1 - 11.3 for study sample size calculations, and a summary of the study analysis plan . Sections 11.4 and 11.5 address the issues of data poolability and missing data. Unless otherwise noted, all statistical tests will be performed at the  $\alpha$  = 0.05 level.

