## 9.7 Missing Data

All statistical tests on the effectiveness endpoints will be performed in two ways: (1) using only those subjects with available required for endpoint analysis and (2) by using the method of last observation carried forward (LOCF). Both methods of analyses will then be compared. However, both methods will be used for the comparison of NYHA classification at 8 year post implant to OPC (75%) and for the comparison of hemodynamic performance one year to baseline for the purpose of investigating the effect of loss-to-follow-up.

NYHA classification and hemodynamic performance will be summarized at each of the follow-up interval. In addition, the NYHA classification will only be statistically compared to OPC at 8 years post implant and only the one year post implant hemodynamic performance will be statistically compared to baseline.

To further demonstrate the impact of lost of the follow-up on the effectiveness calculation; a bootstrapped simulation for missing data imputation will be generated as described below:

For each subject who is alive and for whom NYHA assessment is not available at the 8 year post implant follow up visit (Subject A), the last year for which NYHA data is available will be identified (year X).

This document and the information contained herein is considered Proprietary and Confidential and may not be reproduced, used or disclosed without written permission from Edwards Lifesciences LLC.

Separately, a sub group (Group A) of subjects with the same pre-operative and year X NYHA information as Subject A, available data at 8 year post-implant will be identified.

Subsequently, an observed value from the pool of subjects in sub group A will be selected randomly and used to impute the NYHA classification for subject A at 8 years post implant.

The above steps (1-3) will be performed for each subject who is lost to follow up before the 8 year post implant follow-up visit.

Lastly, steps 1 - 4 above will be repeated 999 times to generate 1000 estimated percentages of subjects with NYHA in classes I or II at 8 years post implant. The central 95th percentile for the 1000 estimated percentages will be calculated.

The central 95th percentile generated by the simulation will reflect the variability in the primary effectiveness endpoint estimate caused by lost to follow up.

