#### **Longitudinal Outcomes**

Time-related events after valve replacement are assumed to occur at an instant in time; however, many outcomes of importance are conditions or processes that evolve with time, such as return of regurgitation after valve repair, change in New York Heart Association functional class (graded or ordinal outcomes), regression of ventricular mass (continuous outcome), and use of warfarin sodium (binary outcome). Values for these outcomes are captured at discrete instances in time ("snapshots"), which may be taken repeatedly at prospectively specified follow-up intervals, cross-sectionally, or opportunistically.

Snapshots are subject to many biases. If a condition changes rapidly but snapshots are taken infrequently, aliasing is introduced. If opportunistic follow-up occurs only when symptoms recur, the prevalence of undesirable change may be overestimated. Change is also related to precision of measurements; for example, degree of mitral regurgitation depends on systolic blood pressure and quality of the echocardiogram. Of course, the entire series of assessments is truncated by death or by removal of the valve of interest.

The challenge in analyzing longitudinal data is estimating the average temporal pattern of outcome and its variability in the group of patients. This average must account for sampling challenges, censoring (truncation) by death, unequal number of repeated measurements of the outcome per patient, variability in time among repeated measurements (such as serial echocardiographic assessment at different intervals after treatment), and the fact that sequential measurements obtained for a given patient will be more correlated with themselves than will measurements between individuals. Thus, these kinds of data, methods of longitudinal data analysis have developed rapidly during the last two decades. These methods include mixed models, random and fixed effects models, generalized estimating equation approach, and hierarchic models (such as currently used for The Society of Thoracic Surgeons National Database risk assessment). Longitudinal data analysis of a series of assessments is superior to analyzing only condition at last follow-up. This methodology is also superior to dichotomizing outcomes and analyzing them with actuarial methods as if they were events, such as freedom from grade 3+ mitral regurgitation after repair.

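### Section 9.5.2 tests paired regurgitation grades with Jonckheere-Terpstra, an independent-groups test, and names neither groups nor sidedness; a minor fault, cured by one named paired ordinal test

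*Combined protocol and SAP*

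**What the plan says.** Section 9.5.2 (Hemodynamic Performance) schedules echocardiograms preoperatively, at one year and at other visits, so each subject can supply a before-and-after pair. It then gives two rules for the one-year comparison:

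- Regurgitation: "Improvement in regurgitation at one year will be analyzed via the Jonckheere-Terpstra test", with a textbook reference on nonparametric methods.
- Everything else: "Change at one year from baseline for all other hemodynamic outcomes will be analyzed using paired" *t*-tests.

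Section 9.7 (Missing Data) confirms the contrast intended. It applies both missing-data methods "for the comparison of hemodynamic performance one year to baseline", and says that only the one-year hemodynamic results are tested against baseline.

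On the level, Section 9.0 has a general rule: "Unless otherwise noted, all statistical tests will be performed at the" 0.05 level. It does not say one- or two-sided. Where the plan chose a direction it said so: Section 9.5.1 tests NYHA class "using a one - sided Binomial exact test".

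Section 9.5 asks for the effectiveness analyses overall and also by valve size (TAD) and valve model. Section 9.5.2 closes by asking for its analyses overall and by model.

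No section says what the ordered groups are for the Jonckheere-Terpstra test, or how the pairing would be handled.

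**The concern.** Jonckheere-Terpstra looks for a trend in a response across independent ordered groups. The question here is whether regurgitation grade fell within subjects between two visits. The test cannot be run as written until someone decides what the groups are, and the two obvious choices behave differently:

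- **Visits as groups.** With two groups the test is Mann-Whitney. It treats the two grades of one subject as coming from different people, so its variance is wrong unless they are uncorrelated.
- **Baseline grade as groups.** The test then asks whether subjects who started worse also finish worse. That is association, not change.

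At stake are the calibration of one secondary p-value, repeated in each stratum, and the freedom to choose groups and direction after the data are seen. The protocol's own Appendix 1, the reporting guideline, notes under Longitudinal Outcomes that "sequential measurements obtained for a given patient will be more correlated with themselves than will measurements between individuals".

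**Working it through.** The plan gives no sample size, power, effect size or correlation for this test, so there is no planned figure to reproduce.

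**1. Level with the two visits as groups.** If nothing changes, both visits share one grade distribution. Let *r* be the within-subject correlation of the mid-rank scores. Mann-Whitney uses a variance proportional to 1, but the true variance of the difference is proportional to 1 - *r*. The actual two-sided level is therefore about 2Φ(-1.96/√(1 - *r*)).

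Inputs: one- to two-year grades for model 6900 (Appendix 4, model 7000TFX instructions, Table 5), summed over sizes. Grade 0 is 2+31+36+17+3 = 89, 1+ is 30, 2+ is 10, 3+ is 2 and 4+ is 0, of 131. Grades come from a latent bivariate normal whose correlation is an assumption. Example at 0.3: *r* = 0.203, 1.96/√0.797 = 2.195, level 2.8%.

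| Latent correlation | *r* of rank scores | Level by formula | Simulated level, 190 pairs |
|---|---|---|---|
| -0.3 | -0.182 | 7.1% | 6.9% |
| 0 | 0 | 5.0% | 5.3% |
| 0.3 | 0.203 | 2.8% | 2.6% |
| 0.5 | 0.355 | 1.5% | 1.5% |

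The signed-rank test held 4.4% to 5.5% in the same simulations.

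**2. Level with baseline grade as groups.** Simulated with 150 pairs and identical assumed grade distributions at both visits (30/30/20/15/5%), so no change at all: the test rejects 90% of the time at correlation 0.3 and 100% at 0.6. With a large real improvement and correlation 0 it rejects only about 4% to 5% of the time. It does not respond to improvement.

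**3. Numbers of pairs.** Section 4.2 reports that "a total of 249 patients had a study valve in place at discharge". In model 6900P (Appendix 4, model 7300TFX instructions, Table 10) 160 of 209 subjects had a one-year grade: 249 × 160/209 = 191, run as 190. The smallest size, TAD 28, had 22/363 implants in model 6900 and 28/209 in 6900P: 250 × 22/363 = 15 and 250 × 28/209 = 33. In 6900P, 20 of 28 at that size had a one-year grade, which gives 15 × 20/28 = 11 and 33 × 20/28 = 24 pairs.

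**4. Power, Mann-Whitney against signed-rank, two-sided 5%.** All scenarios end at the 6900 grades above.

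- *Large change*: preoperative grades mapped by assumption from the 6900 case mix. Stenosis and none (25.1% + 8.3% = 33.4%) are put at grade 0, mixed disease (16.0%) at 2+, and regurgitation (50.7%) split equally between 3+ and 4+.
- *Modest* (50/25/15/8/2%) and *small* (60/24/10/5/1%): assumed outright.

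| Scenario | Pairs | Correlation 0 | Correlation 0.5 |
|---|---|---|---|
| Large | 190 | 100% vs 100% | 100% vs 100% |
| Large | 24 | 96% vs 99.5% | 98% vs 100% |
| Large | 11 | 69% vs 78% | 72% vs 90% |
| Modest | 24 | 32% vs 35% | 27% vs 53% |
| Small | 190 | 48% vs 63% | 49% vs 86% |

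The zero-correlation gap in the last row is not a pairing effect. It arises because signed-rank gives more weight to large drops in grade: a paired sign test in the same setting has 44.5% against 48.2% for Mann-Whitney. The echo grading scale in this study differs from the 6900 scale, so all these distributions are illustrative.

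**The case against.** The best defence is that little depends on this test. Hemodynamic performance is a secondary endpoint, and Section 3.3.4 lists it at 8 years, so the one-year comparison is not even the listed time point. Section 9.5.2 already tabulates the frequency of each severity grade by interval, no sample size or decision rule uses the p-value, and the word improvement implies a direction. Size-stratified testing rests only on the general reporting sentence in Section 9.5. The textbook cited for the method is not available here, so how the sponsor would apply the test is inferred. All of this stands, and it limits the severity.

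Three stronger readings are tempting, and the documents support none of them:

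- *The main cost is lost power.* This needs a clearly positive correlation, which the documents do not give. The Appendix 1 remark concerns serial measurements in general; here the diseased valve is removed between the two echoes, and the correlation could be near zero. The visible losses also need assumed small or modest changes. The predecessor case mix, with 50.7% + 16.0% = 66.7% regurgitation or mixed disease in model 6900, points to a large change.
- *The test inflates false positives.* Only at negative correlation, which no section suggests.
- *The test does not address improvement at all.* True if baseline grade defines the groups, but no section says that it does.

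The defence does not explain why an independent-groups test is used for the one ordinal outcome when the next sentence pairs all the others.

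**Conclusion.** The point holds as a minor fault. The named test does not fit the paired comparison that Sections 9.5.2 and 9.7 describe, and its groups and sidedness are undefined. On the two-visit reading its true level is about 1.5% at correlation 0.5, 2.6% at 0.3, nominal at zero and 7% at -0.3, with power lost if the correlation is positive. On the baseline-grade reading it tests something else.

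The omission of groups and sidedness is certain from the text. The size of the effect is not: the correlation, the preoperative grades and the stratum sizes are assumptions, and with correlation near zero there is no miscalibration. For the large improvement expected in the full cohort both tests reject practically always. The choice can matter for a small overall change or in a small stratum such as TAD 28. Neither primary endpoint nor the sample size is touched.

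**What to change.** In Section 9.5.2 replace Jonckheere-Terpstra with one test: the Wilcoxon signed-rank test on each subject's change in regurgitation grade from the preoperative to the one-year echocardiogram. State whether it is one- or two-sided. Report the baseline-by-one-year shift table beside it, overall and in the strata already planned.

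Name only this test. An unscored test of marginal homogeneity is also paired but could lose power in the small strata, and leaving a choice open would repeat the ambiguity.

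The cost is one sentence of plan wording and one table. The echocardiograms are already scheduled, so no new data, visits or subjects are needed.
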